8.1.2 Expansion Phase

The expansion phase will require an amendment to this protocol after the escalation phase has been successfully completed to investigate the treatment with RGT100-PEI in additional 15 subjects in up to 4 different tumor indications (up to 60 subjects in total). The expansion phase will continue to be conducted according to the same Groups (Group A for cutaneous lesions and Group B for liver lesions) and according to the same treatment and examination schedule as the escalation phase.

Following the escalation phase all available safety and efficacy data as well as feasibility will be assessed and summarized in a safety report. This report will also include the selection and justification for the planned tumor indications as well as the RP2D for the expansion phase. The safety report together with an amended protocol will be submitted to authorities and the expansion phase will only start if the proposed RP2D and tumor indications are accepted by authorities.

8.1.3 Extended Treatment Period

Subjects with partial response (PR) or stable disease (SD) at 8 weeks and no clinical deterioration will be allowed to be treated with a second cycle of RGT100-PEI for an additional 4 weeks. This will be based on Investigator decision and subject agreement, both documented in the subject file and electronic case report form (eCRF).

These subjects must have completed initial participation with acceptable toxicity. During further therapy, subjects will continue to be assessed for safety and tolerance, as well as for preliminary evidence of anti-tumor efficacy of RGT100-PEI. For details of study assessments to be performed for the extended treatment period, refer to [Appendix 17.1](#) (Group A) and [Appendix 17.2](#) (Group B).

8.2 Discussion of Study Design

The study is designed as a Phase I/II, open-label, repeat dose escalation study of RGT100-PEI in subjects with advanced or recurrent tumors. The data will be used to assess safety, tolerance, and tumor response of repeat doses of RGT100-PEI.

The study design exposes a small number of subjects to each dose of RGT100-PEI and uses different subjects for each cohort. A low starting dose is used to evaluate safety with minimal

risk to subjects. Initially a single subject will be dosed, 1 week before dosing the remaining subjects in the cohort.

A SRC will meet to review the safety results from a given cohort, before escalating to the next dose in a new cohort. Refer to [Section 10.5](#) for SRC details.

A conventional 3 + 3 design is considered a safe design for a dose escalation study in this subject population.

Frequent assessments of safety will be conducted to support the primary objective for conducting the study. The Investigator will review safety and tolerability data to ensure that subjects will only receive another dose of RGT100-PEI in the subsequent treatment period if the dose is being tolerated. Dose escalation meetings will be held to review safety and tolerability data for all subjects before dose escalation and before entering the expansion phase.

Tumor response also will be assessed to support the secondary and exploratory objectives of the study.

No placebo arm is offered to this subject population for ethical reasons.

8.3 Selection of Study Population

8.3.1 Number of Planned Subjects

The number of subjects enrolled in the dose escalation phase will depend on the number of DLTs observed in each cohort and the number of DLs evaluated. Approximately 9 to 24 subjects are planned to be treated each in Group A (cutaneous lesions) and Group B (liver lesions) during dose escalation.

In the expansion phase, an additional 60 subjects (4 groups of 15 subjects each) in each tumor-specific group (60 subjects in total) will be treated at the RP2D for further tolerability and preliminary efficacy assessments. No formal power calculations were performed to obtain the suggested sample size. During further therapy, subjects will continue to be assessed for safety and tolerance, as well as for preliminary evidence of anti-tumor efficacy of RGT100-PEI. Hence the number of subjects has been based on the desire to obtain adequate safety, tolerability, anti-tumor activity, and PK data while exposing as few subjects as possible to the investigational product and procedures.

The tumor type to be included in each cohort will be determined following the completion of the dose escalation phase and will be based on the preliminary anti-tumor activity results from dose escalation. The expansion phase is not intended to provide definitive results but will give a better indication of safety in the chosen subject population and will provide preliminary efficacy data.

If a subject does not meet the list of key inclusion/exclusion criteria the first time, re-screening is allowed, as long as dose escalation or expansion phase is recruiting.

8.3.2 Inclusion Criteria

A subject will be eligible for inclusion in this study if all of the following criteria apply:

1. Male or female aged ≥ 18 years

2. Subjects with histologically or cytologically confirmed diagnosis of advanced or recurrent tumors (including lymphomas) for whom all standard treatments have been used or are not feasible or RGT100-PEI is a suitable treatment option and:
 - a. For Group A: has cutaneous, SC, or lymph node injectable tumors
 - b. For Group B: has injectable liver tumors or liver metastases
3. Eastern Cooperative Oncology Group (ECOG) performance status 0-2
4. Life expectancy > 3 months as assessed by the Investigator
5. Adequate organ function:
 - a. Bone marrow function: Hemoglobin ≥ 10 g/dL (pre-treatment transfusion allowed); lymphocyte count $\geq 0.5 \times 10^9/L$; absolute neutrophil count $\geq 0.5 \times 10^9/L$; platelet count $\geq 75 \times 10^9/L$
 - b. Hepatic function: AST and ALT $\leq 2 \times$ upper limit of normal (ULN) ($3 \times$ ULN in the case of liver metastases); bilirubin $\leq 1.5 \times$ ULN ($2 \times$ ULN in case of liver metastases)
 - c. Renal function: creatinine $< 1.5 \times$ ULN and/or creatinine clearance ≥ 50 mL/min (Cockcroft and Gault)
6. Negative serum pregnancy test within 2 weeks before first dose of study drug if the subject is a woman of childbearing potential. Subjects and subjects' partners of childbearing potential must agree to use birth control consistently and correctly during the study and for at least 6 months after the last study drug application.
7. At least 1 measurable lesion per RECIST 1.1 and 1 separate injectable lesion with diameter ≥ 1 cm but < 7 cm
8. Ability to provide written informed consent before any study drug-related screening procedures being performed

8.3.3 Exclusion Criteria

A subject will not be eligible for the trial if any of the following apply:

1. Any tumor-directed therapy within 4 weeks before study treatment
2. Treatment with investigational drugs within 4 weeks before study enrolment
3. Systemic steroids at a dose of > 10 mg of prednisolone, > 2 mg of dexamethasone a day or equivalent, except topical (inhaled, topical, nasal) for the last 28 days and ongoing
4. Subjects with rapidly progressing disease (as determined by the Investigator)
5. Ongoing immune-related adverse events (irAEs) and/or AEs \geq grade 2 not resolved from previous therapies except vitiligo, stable neuropathy grade 2, hair loss, and stable endocrinopathies with substitutive hormone therapy
6. Within 4 weeks of major surgery
7. Prior splenectomy
8. Documented history of active autoimmune disorders requiring systemic immunosuppressive therapy

9. Primary or secondary immune deficiency
10. Active allergy requiring systemic medication or active infections requiring anti-infectious therapy
11. Seropositive (except after vaccination) for human immunodeficiency virus (HIV), hepatitis B virus (HBV) or hepatitis C virus (HCV)
12. Clinically significant cardiac disease including heart failure (New York Heart Association, Class III or IV), pre-existing arrhythmia, uncontrolled angina pectoris, or myocardial infarction within 1 year before study entry
13. Dementia or altered mental status that would prohibit informed consent
14. Other severe, acute, or chronic medical or psychiatric condition or laboratory abnormality that may increase the risk associated with study assessed by the Investigator
15. History of stroke, seizures, encephalitis, or multiple sclerosis
16. Gastric ulcer or inflammatory bowel disease or Crohn's disease or ulcerative colitis in the last 6 months
17. Active drug or alcohol abuse
18. Pregnant or breast feeding

8.3.4 Removal of Subjects From Therapy or Assessments

8.3.4.1 Subject Withdrawal

Subjects may stop study drug for any of the following reasons:

- Subject request
- Use of non-permitted concurrent therapy
- Non-compliance with the study drug or study schedule
- Lost to follow-up
- Occurrence of AEs not compatible with the continuation of the study, in the Investigator's opinion, or unacceptable to the subject to continue
- Investigator request
- Intercurrent illness
- Sponsor request
- Treatment failure

Subjects are free to withdraw from the study at any time without providing reason(s) for withdrawal and without prejudice to further treatment. The reason(s) for withdrawal will be documented in the eCRF.

Subjects withdrawing from the study will be encouraged to complete the same final evaluations as subjects completing the study according to this protocol, particularly safety

evaluations. The aim is to record data in the same way as for subjects who completed the study.

Reasonable efforts will be made to contact subjects who are lost to follow-up. These efforts must be documented in the subject's file. The reason for early withdrawal from treatment should be clearly documented in the medical records. An end of treatment visit assessment should be performed and the results of the evaluations and observations reported in the eCRF.

Consent withdrawal means that a subject has expressed a wish to withdraw from the study. Under these circumstances, the site needs to document all relevant discussions in the subject notes and notify the contract research organization (CRO), which will allow the CRO to mark all future eCRFs as not applicable. Under these conditions, Investigators are still responsible to follow up any SAEs until resolution.

The Sponsor has the right to terminate the study at any time in case of SAEs or if special circumstances concerning the study drug RGT100-PEI or the company itself occurs, making further treatment of subjects impossible. In this event, the Investigator(s) will be informed of the reason for study termination.

8.3.4.2 Subject Replacement

Subjects who do not comply with the protocol or who withdraw consent may be replaced.

In the dose escalation phase, a subject will not be replaced if they come off treatment due to a DLT. They are, however, not evaluable (NE) for the primary endpoint if they withdraw for other reasons than safety/toxicity before completing 4 weeks of treatment (the DLT period), and will need to be replaced. Withdrawn subjects will not receive further treatment with RGT100-PEI, but will be followed up unless they withdraw consent.

If subjects in Group A miss more than 2 injections or subjects in Group B miss more than 1 injection due to drug-related toxicity (but not qualifying for a DLT), these subjects will be replaced in the corresponding group for the purpose of DLT evaluation.

In the expansion phase, subjects are evaluable if they have received at least 1 injection of RGT100-PEI. Non-evaluable subjects for the primary endpoint of assessment of toxicity may be replaced.

8.3.4.3 Pregnancy

Pregnancies (in a participant or partner) occurring while participating in this trial require expedited reporting. A pregnancy form should be completed and faxed to INC Research Safety & Pharmacovigilance within 24 hours of the Investigator becoming aware of the pregnancy. All reported pregnancies should be followed and the outcome reported using the same form. If an AE occurs in relation to the pregnancy, it has to be noted on the pregnancy form and recorded within the eCRF. If an SAE occurs in relation to the pregnancy, it has to be noted on the pregnancy form, recorded within the eCRF, and immediately reported to INC Research Safety & Pharmacovigilance as described in [Section 10.4.4.3](#).

The Investigator must make all reasonable efforts to follow the pregnancy until its end and will report all outcomes associated with the pregnancy to the Sponsor. If the outcome of the pregnancy meets any of the criteria for seriousness, it must also be reported as an SAE. Examples of pregnancy outcomes that are SAEs include reports of:

- Congenital anomalies or developmental delay, in the fetus or the child

- Fetal death and spontaneous abortion
- Suspected adverse reactions in the neonate that are classified as serious

In the situation of pregnancy of the female partner of a male study subject, consent for the release of medical data should be obtained from the female partner to allow collection of information on the outcome of the pregnancy.

Women who become pregnant should be withdrawn from trial treatment immediately.

8.3.5 Protocol Deviations and Waivers to Entry Criteria

Protocol adherence is a fundamental part of the conduct of a clinical study. Changes to the approved protocol need prior approval unless for urgent safety reasons.

Systems for prospectively approving protocol deviations, in order to effectively widen the scope of a protocol must not be used. Doing so might erode the scientific and ethical value of the protocol and its authorization and might have an impact on the processes put in place for the care and safety of the study subjects.

Investigators must contact the CRO to obtain guidance and/or clarification as necessary if unsure whether the subject satisfies all the entry criteria and to clarify matters of clinical discretion. The CRO will contact the Sponsor or Lead Investigator as necessary.

Protocol waiver to enter a subject who does not satisfy the selection criteria are not allowed. The Investigator must document and explain any deviations/violations from the approved protocol. The Investigator should promptly report any important violations that might impact subject safety, data integrity, or be a possible serious breach (refer to [Section 11.3](#)) to the Sponsor/CRO.

8.4 Investigational Products

8.4.1 Investigational Products Administered

RGT100-PEI is to be administered by intratumoral/intralesional injection into cutaneous, subcutaneous, nodal and or intrahepatic lesions that are visible, palpable or detectable by imaging guidance (eg, ultrasound).

In Group A: RGT100-PEI will be administered into cutaneous, subcutaneous or nodal lesions by trained site staff.

In Group B: RGT100-PEI will be administered into liver lesions under image guidance (eg, ultrasound) by a radiologist or another experienced physician.

There will be no interruption between treatments, except as described in the dose modification and dose delay section ([Section 8.4.8.4](#)).

8.4.1.1 Injection of RGT100-PEI – Tumor Selection

Injections should be targeted at viable tumor tissue and not at necrotic tissue. The Investigator may use his or her judgement to determine which tumors are accessible and injectable, and select an index lesion for injection. The accessibility and injectability will be assessed in accordance with routine medical practice (e.g., by physical palpation [SC lesions], by ultrasound or computerized tomography [CT] guidance if necessary [liver lesions]; in Germany only ultrasound guidance may be used). There will be documentation of the method

of assessment and various characteristics of the selected lesion (presence or absence of necrosis, ulceration, progression and prior local therapies).

It is up to the Investigator's discretion to select the index lesion and the lesion that serves as reference lesion.

There should be at least 1 measurable lesion left untreated, to meet the secondary endpoint of assessing changes in untreated disease and for irRECIST-assessment.

There is no limit to the proximity of the lesions selected for injection, except:

- Injected lesion(s) must be clearly distinguishable
- The un-injected lesion selected for observation (reference lesion) must be sufficiently remote from an injected lesion to allow for evaluation over a 60/90 day duration of the study.

The Investigator should make all efforts to apply the whole volume of drug into the chosen index lesion especially during the escalation phase.

The total volume of drug should be injected into the chosen index lesion. All lesions will be injected either directly or under image guided control (e.g., ultrasound). At each injection, the operator should collect the following information:

- Location of the lesion in the body
- Size of the injected lesion
- NCI CTCAE grading inflammation at the site and time of injection, if any, before and after injection
- Type of lesion injected (skin, lymph node, liver)
- Planned volume to be injected in the lesion (for eventual intent-to-treat analysis)
- Actual volume injected in the lesion (for eventual per dose received analysis)

The total volume of the corresponding dose level should be injected into the chosen index lesion. Only in cases where this is not possible the investigator will be allowed to split the total volume of a DL and inject the remaining volume into another lesion. The total volume of the applicable DL must not be exceeded.

In the instance that a lesion exhibits complete response (CR) during the 4 weeks of therapy, the Investigator will be allowed to choose additional lesions for injection. The Investigator always needs to document which lesion(s) has/have been injected.

In order to avoid a non-injected target lesion becoming an injected lesion (and therefore rendering a subject as non-interpretable), it will be required that during the screening period the radiologist and the interventional radiologist (or Investigator) define together the non-injected lesions to be followed by irRECIST and list by priority order the lesion to be injected during the treatment.

Depending on the specific dose level and thus the amount of volume to be injected, the investigator should choose the index lesion for injection accordingly based on its size. The following algorithm below should be used as a guidance. However, it is up to the investigator to select an appropriate index lesion considered feasible for the volume to be injected, which may also be a bigger or smaller lesion.

- Dose level 1: 1.0 mL for lesions of 1.0 to 2.0 cm longest diameter
- Dose level 2: 2.0 mL for lesions of > 2.0 to 3.0 cm longest diameter
- Dose level 3: 3.0 mL for lesions of >3.0 to 5.0 cm longest diameter
- Dose level 4: 4.0 mL or more for lesions > 5 to 7 cm longest diameter

The measurement will be of the longest diameter of vital tumor tissue. In the event that it is not possible to assess the discrete size of the vital tissue, the maximum volume injectable should be pro-rated according to the percentage composition of necrotic tissue. The Investigator should also consider the tumor type and the tumor density in determining the lesion to be injected at the corresponding dose level.

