
Study Parameters
	
Safety and tolerability: The safety and tolerability of intratumoral/intralesional injections of RGT100-PEI will be evaluated by the incidence of AEs (all AEs will be evaluated according to NCI-CTCAE version 4.03), serious adverse events (SAEs), dose-limiting toxicities (DLTs), and use of concomitant medications. Safety assessments will include: electrocardiograms (ECGs), physical examinations, ECOG performance status, vital signs and clinical laboratory samples (hematology, biochemistry, cytokines and urinalysis).
 
Anti-tumor activity: To explore the anti-tumor activity of RGT100-PEI on injected and un-injected tumor lesions will be evaluated with the following assessments: Tumor assessments, imaging, tumor biopsies to evaluate immunogenic cell death and immune infiltration of injected tumors. Tumor response rate will be evaluated radiologically using immune-related RECIST criteria (irRECIST).
 
Pharmacokinetic: The PK of RGT100-PEI will be measured from blood samples collected at the start and end of the study. Standard PK parameters will be determined from the RGT100-PEI concentration in plasma.

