7 STUDY OBJECTIVES AND ENDPOINTS

7.1 Objectives

The primary objectives of the study are to:

- Evaluate the safety and tolerability of intratumoral/intralesional injections of RGT100-PEI
- Determine the recommended Phase 2 dose (RP2D) feasible for intratumoral/intralesional injections of RGT100-PEI

The secondary objective of the study is to:

- Explore preliminary anti-tumor activity of RGT100-PEI on injected and un-injected tumor lesions

The exploratory objectives of the study are to:

- Investigate the type of cytokine release in plasma upon treatment
- Investigate the pharmacokinetics (PK) of RGT100-PEI in subjects with advanced or recurrent tumors
- Explore potential predictive biomarkers of tumor responses upon intratumoral/intralesional RGT100-PEI therapy*
- Evaluate the impact of RGT100-PEI therapy on immune infiltration of injected tumors*

*These exploratory objectives will be evaluated in a separate sub-study. Results of these exploratory investigations will not be presented as part of the main Clinical Study Report.

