7.2 Endpoints

The primary endpoints of the study are:

- Incidence and severity of treatment-related adverse events (AEs) and laboratory abnormalities, graded according to National Cancer Institute Common Terminology Criteria for Adverse Events (NCI CTCAE) version 4.03 criteria
- Occurrence of serious adverse events (SAEs)
- Occurrence of treatment discontinuation due to treatment-related AEs
- Incidence and severity of dose-limiting toxicities (DLTs)

The secondary endpoint of the study is:

- Objective response rate as evaluated radiologically using immune-related Response Evaluation Criteria in Solid Tumors (irRECIST)

The exploratory endpoints of the study are:

- Type of cytokine release in plasma
- Plasma concentrations of RGT100-PEI and, where feasible, standard PK parameters
- Presence of predictive biomarkers of tumor responses*
- Evidence of immune infiltration of injected tumors*

*These exploratory objectives will be evaluated in a separate sub-study. Results of these exploratory investigations will not be presented as part of the main Clinical Study Report.

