11.1.4 Efficacy Variables

11.1.4.1 Tumor response

Tumor response will be assessed to support the secondary objectives of the study. Tumor response data will be listed and summarized by cohort and visit (that includes disease assessment) using the following response categories: CR, PR, SD, PD, NE, early death from malignant disease, early death from toxicity, early death from other cause, or unknown (not assessable, insufficient data). The results of lesion measurements, changes in size and supportive laboratory parameters will be analyzed and summarized. Evaluations at screening and at Day 1 will serve as baseline values. Changes from baseline for continuous variables and shift tables for categorical variables will be presented by cohort and by visit of tumor assessment. Descriptive statistical methods as outlined in detail in the SAP will be used.

Objective response rate as defined by achieving CR or PR will be presented by percentage rates and 95% confidence intervals assuming an exact binomial distribution (Clopper–Pearson method). Fisher’s exact test (univariate analyses) and logistic regression may be used to compare the response rates of the different cohorts.

The duration of response (DR) will only be calculated for subjects who have an objective response. The DR is calculated from the date of the first documented response until the date of progression or death; subjects who continue to respond at the date of data cut-off (last subject last visit) will be censored at their last known date. Summaries of DR (n, medians, quartiles) will be provided.

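### The secondary objective covers injected and un-injected lesions, but the only listed endpoint is one overall irRECIST response rate, and the plan neither splits results by injection status nor says whether injected lesions count in the tumor burden

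*Combined protocol and SAP*

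**What the plan says.** - **Objective (7.1).** "Explore preliminary anti-tumor activity of RGT100-PEI on injected and un-injected tumor lesions".
- **Endpoint (7.2).** The only secondary endpoint is "Objective response rate as evaluated radiologically using immune-related Response Evaluation Criteria in Solid Tumors (irRECIST").
- **Endpoint presumed in 8.4.1.1.** "There should be at least 1 measurable lesion left untreated, to meet the secondary endpoint of assessing changes in untreated disease and for irRECIST-assessment". Section 7.2 lists no such endpoint.
- **Synopsis, Study Parameters.** Activity "on injected and un-injected tumor lesions will be evaluated with the following assessments: Tumor assessments, imaging, tumor biopsies". The only summary measure named there is the irRECIST response rate.
- **Analysis (11.1.4.1).** Response categories and lesion measurements are to be summarised. "Changes from baseline for continuous variables and shift tables for categorical variables will be presented by cohort and by visit of tumor assessment". There is one response rate (CR or PR) with a Clopper-Pearson interval. Injection status is not mentioned.
- **Lesion designation (8.4.1.1).** At screening the radiologist and the interventional radiologist or investigator must "define together the non-injected lesions to be followed by irRECIST" and rank the lesions to be injected. The stated reason is "In order to avoid a non-injected target lesion becoming an injected lesion (and therefore rendering a subject as non-interpretable").
- **Response criteria (17.4).** Up to five target lesions form the total measured tumor burden (TMTB). Neither target selection nor the TMTB definition refers to injection status.

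**The concern.** A secondary objective with two parts needs an endpoint, or a breakdown of one, that can answer each part. Here one subject-level rate has to serve both, and what it measures depends on a rule that 17.4 does not state. For a locally injected agent meant to act systemically, the two parts answer different questions: does the injected lesion shrink, and does disease elsewhere respond? Sections 8.3.1 and 11.1.7 use activity seen in escalation to choose the expansion indications. If sites apply different rules on the index lesion, their recorded categories are not comparable when that choice is made.

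**Working it through.** The plan gives no figure to reproduce. The check sets the sections side by side and then applies the response rules in 17.4.

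**1. From objective to analysis**

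| Step | Injected lesions | Un-injected lesions |
|---|---|---|
| Objective (7.1) | yes | yes |
| Endpoint presumed in 8.4.1.1 | not named | yes |
| Endpoint listed in 7.2 | overall rate only | overall rate only |
| Summary in 11.1.4.1 | not separated | not separated |

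**2. Is the injected lesion a target?** Section 8.4.1.1 points towards following the un-injected lesions. It does not say that only these count. Sections 10.1.1.1 and 10.1.1.2 require one measurable lesion of each kind and follow-up of every target lesion. None of these, nor 17.4, settles what enters TMTB.

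**3. Reading A: the injected lesion is non-target.** Under 17.4, measurable lesions not chosen as targets are non-target, and non-target lesions do not influence irPR or irSD. TMTB is then the un-injected sum R.
- Index shrinks by anything from 0 to 100%, R unchanged: TMTB change = 0%, so irSD and no response.
- R falls by at least 30%, no progression: irPR, whether or not the index lesion shrinks.
- All un-injected disease disappears: a persisting index lesion makes this irPR instead of irCR. Both count in the response rate.

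Shrinkage of the injected lesion therefore shows only in the split between irCR and irPR. Massive, unequivocal worsening of it could still give irPD.

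**4. Reading B: the injected lesion is in TMTB.** Let d be its baseline contribution, R the un-injected target sum and k = R/d. Assume no new measurable lesions and no progression of non-target disease.

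- Index shrinks by fraction s, R unchanged: TMTB change = −s·d/(d + R) = −s/(1 + k). irPR needs s ≥ 0.30(1 + k).
- R falls by fraction u, index unchanged: irPR needs u ≥ 0.30(1 + 1/k).

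The documents do not give k, so a range is shown:

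| k = R/d | Index shrinkage that alone gives irPR | Un-injected shrinkage that alone gives irPR |
|---|---|---|
| 0.5 | 0.30 × 1.5 = 45% | 0.30 × 3 = 90% |
| 1 | 0.30 × 2 = 60% | 0.30 × 2 = 60% |
| 2 | 0.30 × 3 = 90% | 0.30 × 1.5 = 45% |

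Index shrinkage alone can give irPR whenever 0.30(1 + k) ≤ 1, that is, k ≤ 7/3 (about 2.33). The rate then mixes the two kinds of lesion.

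**5. Same scans, two categories.** With k = 1, index shrinkage of 60% and un-injected lesions unchanged, Reading A gives 0% and irSD. Reading B gives −0.60/2 = −30% and irPR.

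**6. Can the split be made from planned data?** Section 10.1.1.1 has all measurable lesions measured on the scan reports, 10.1.1.2 has them re-measured, and 8.4.1.1 has injected lesions documented. The split needs no new scans, provided per-lesion values reach the database. The eCRF entry that 10.1.1.2 names is the overall category.

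**7. Precision.** For 0 of 6 subjects the Clopper-Pearson upper limit is 1 − 0.025^(1/6) = 45.9%. For 3 of 15 the interval is 4.3 to 48.1%.

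**The case against.** The strongest reply has four parts.

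- **The detail may come in the SAP.** Sections 11.1, 11.1.4.1 and 11.1.5 defer methods to a separate SAP that is not in these documents, and it could add the split. This stands as a limit on the point. It does not put the missing endpoint into 7.2 or tell sites which lesions to choose at screening.
- **Lesion-level summaries are planned.** Section 11.1.4.1 covers lesion measurements and size changes as well as the response rate. That is correct. What is missing is the stratifier, so the remedy is small.
- **The rule is already in 8.4.1.1, and 17.4 is only a quick reference.** In part this is fair. However, 8.4.1.1 does not say that only un-injected lesions count, and its mention of a non-injected target lesion could imply that injected targets exist.
- **The study is exploratory.** There are 3 to 6 subjects per dose level and no power calculation for the expansion, so any added proportion will be imprecise. That stands.

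A reader might also infer three stronger claims, none of which the documents support:

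- **That a later SAP could not repair inconsistent target choices.** Since all measurable lesions are measured and re-measured, sums could be rebuilt by injection status if per-lesion data are captured.
- **That the injected lesion in Group A lacks a baseline size.** Section 8.4.1.1 records lesion size at each injection, the footnotes to Table 3 schedule caliper measurement at baseline and Day 1, and 11.1.4.1 treats Day 1 as baseline.
- **That 8.4.1.1 and 17.4 contradict each other.** This is an unstated rule. Nor are subjects whose un-injected target is later injected without any possible category: the not-evaluable and unknown categories exist, though no rule assigns such subjects to them.

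**Conclusion.** The point holds as a gap in endpoint and analysis definition, and it should be corrected. On the text supplied, the overall response rate cannot report both halves of the secondary objective under either reading. Under Reading A it is blind to shrinkage of the injected lesion. Under Reading B it merges the two kinds, and index shrinkage alone can make a responder for any k up to about 2.33.

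Reading A fits 8.4.1.1 better, but that is a judgement, and the conclusion does not depend on it. The Reading B figures are consequences of the 30% rule under assumed ratios with the other lesions unchanged; they do not estimate an effect in this trial. No sample size or error rate is affected. The conclusion could soften once the separate SAP is seen, but the mismatch between 8.4.1.1 and 7.2 would remain.

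**What to change.** 1. **Section 7.2:** list the untreated-disease endpoint that 8.4.1.1 already presumes.
2. **Appendix 17.4:** state, consistently with 8.4.1.1, whether an injected lesion may be a target lesion and enter TMTB.
3. **Section 11.1.4.1:** keep the overall response rate. Beside it, report by visit the percent change from baseline in the sum of diameters, separately for injected and un-injected lesions. Fix both sets by the screening designation, so that the baseline sum does not change between visits. Grouping by what has actually been injected at each scan would let lesions change sets after events related to response, because 8.4.1.1 and 8.4.1.4 allow other lesions to be injected after a lesion's complete response or shrinkage.
4. **Descriptive addition:** give the proportion with at least a 30% decrease in the designated un-injected lesions, with a Clopper-Pearson interval, in a named analysis set.
5. **Later-injected lesions:** report how many subjects had a designated un-injected lesion injected later, with a sensitivity summary excluding them.
6. **Data check:** confirm that per-lesion measurements from the scan reports reach the database.

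The cost is wording in three sections and a few descriptive tables, with no new scans or subjects. The intervals will be wide and should be presented as description only. The amendment that 8.1.2 already requires before expansion is one possible vehicle, although the 17.4 rule is also needed for screening during escalation.
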